## **1.2.4.** Pharmacokinetic Profile of Inhaled Treprostinil

Two studies characterized the pharmacokinetic (PK) profile of single doses of inhaled treprostinil in healthy volunteers. Eighteen subjects were enrolled in a 3 period crossover bioavailability (BA) study. The absolute BAs of the inhaled treprostinil 18 and 36  $\mu$ g were compared to a 15-ng/kg/minute (60 minute) IV infusion of treprostinil. Forty subjects were enrolled in a maximum tolerated dose (MTD) study of 54, 72, 78, 84, and 90  $\mu$ g of inhaled treprostinil. Maximum observed plasma concentration (Cmax), time of the maximum observed plasma concentration-time curve (AUC) from time zero to infinity (AUC0-∞) were determined in both studies.

In the bioavailability (BA) study,  $C_{max}$  and  $AUC_{0-\infty}$  were dose proportional following a single administration of inhaled treprostinil 18 or 36 µg and resulted in 64% and 72% absolute systemic BA, respectively. The mean  $t_{max}$  was 0.15 hours for both inhaled doses.

In the MTD study, inhaled treprostinil was dose proportional for  $AUC_{0-\infty}$  (mean range: 0.661 to 1.579 ng\*hr/mL) and  $C_{max}$  (mean range: 790 to 1708 pg/mL). The mean  $t_{max}$  was 0.20 hours across all doses. Adverse events (AEs) of chest pain, chest discomfort, nausea, and vomiting in the 90 µg cohort were determined to be intolerable; thus the MTD for a single dose of inhaled treprostinil was 84 µg.

Protocol	CONFIDENTIAL
	Protocol Number: PBI L606_2.0

Inhaled treprostinil remained detectable in the plasma approximately 4 hours after inhalation in both studies. Apparent plasma terminal elimination half-life ( $t_{1/2}$ ), calculated using a noncompartmental model, ranged from 0.46 to 0.76 hours across both studies.

## 1.3. Liposomal Treprostinil-related Potential Toxicity and Pharmacokinetics

Many studies have established the high biocompatibility and biodegradability of liposomes as drug carriers in inhaled formulations. The L606 solution is composed of liposomes encapsulating the treprostinil in sodium citrate-bicarbonate buffer. The liposomes are composed of hydrogenated soybean phosphatidyl choline, cholesterol, and distearoyl phosphatidyl glycerol. In addition to the treprostinil-related toxicity observed in the approved products, the liposomal treprostinil is speculated to be involved only with potential respiratory-related toxicity.

The L606 liposomes, with mean diameter >100 nm, are inhaled and reside in the lung. It is believed that treprostinil is released from inhaled liposomes in situ in the lung and adsorbed into the blood. Once released from liposomes in the pulmonary system, treprostinil is expected to follow the same absorption, distribution, metabolism, and excretion pathways as free drug, as previously demonstrated for Tyvaso, Remodulin, and Orenitram. Bioavailability of treprostinil in L606 was compared with treprostinil solution in terms of plasma AUC in rat. Intratracheal administration was used to reduce the effects of aerosol size distribution and nebulizer device. It was found that the 2 formulations are proportional to the applied doses. No saturation phenomena were observed within the tested dose range. The presence of liposome did not affect BA of released (free) treprostinil. Liposomal treprostinil demonstrated sustained release in the pulmonary system as compared to the immediate release of treprostinil solution. It was also indicated that release of treprostinil is triggered by simulated lung fluid and lung surfactant. In contrast, only 5% of treprostinil was released from liposome in the simulated nasal fluid within 8 hours.

### 1.4. Potential Benefits of L606 (Liposomal Treprostinil Inhalation Solution)

The actual concentration of drugs reaching resistance vessels may be greater with targeted delivery by aerosol. As shown in rat toxicokinetic studies, inhaled treprostinil is rapidly absorbed by the lung. After crossing the pulmonary epithelium, the drug may diffuse into the blood or be collected by the pulmonary lymphatic fluid. Accordingly, treprostinil may reach resistance vessels without systemic circulation.

The long duration of pulmonary vasodilation after a single inhalation of treprostinil may be partially explained by the stability of this prostanoid. It is theorized that L606 is deposited in the lung after inhalation, providing a slow release from the alveolar lining layer or the interstitial compartment to the pulmonary vascular smooth muscle cells.

### 1.5. Study Rationale

This is the first-in-human study for L606. The principal aim of this study is to obtain safety and tolerability data when L606 is administered as an oral inhalation as single doses to healthy

subjects. This information, together with the PK data of treprostinil after administration of L606, will help establish the doses and dosage regimen suitable for administration to patients.

### 1.6. Benefit-risk Assessment

Tyvaso inhibits platelet aggregation and increases the risk of bleeding. Subjects with increased bleeding risk will be excluded from this study.

Coadministration of a cytochrome P450 2C8 enzyme inhibitor (eg, gemfibrozil) may increase exposure (both  $C_{max}$  and AUC) to treprostinil. Increased exposure is likely to increase AEs associated with treprostinil administration. Overall, concomitant medications are not allowed during the study (Section 6.1). Also see the exclusion criteria for medication/product restrictions prior to Check-in (Section 4.2).

Healthy subjects in the current study will not receive any health benefit (beyond that of an assessment of their medical status) from participating in the study. The risks of participation are primarily those associated with adverse reactions to the investigational medicinal product (IMP), although there may also be some discomfort from collection of blood samples and other study procedures. More information about the known and expected benefits, risks, and reasonably anticipated AEs associated with L606 may be found in the Investigator's Brochure.

#### 2. OBJECTIVES AND ENDPOINTS

#### 2.1. Objectives

The primary objective of the study is:

• To evaluate the safety and tolerability of single ascending doses of treprostinil after administration of L606 in healthy subjects.

The secondary objective of the study is:

• To assess the PK profile of single ascending doses of treprostinil after administration of L606 in healthy subjects.

#### 2.2. Endpoints

#### 2.2.1. **Primary Endpoints**

The primary safety endpoints for this study are as follows:

- incidence and severity of AEs
- incidence of serious AEs (SAEs)
- vital sign assessments (supine blood pressure, supine pulse rate, and respiratory rate)
- 12-lead electrocardiogram (ECG) parameters
- incidence of laboratory abnormalities, based on hematology, clinical chemistry, and urinalysis test results
- physical examinations.

### 2.2.2. Secondary Endpoints

The single ascending dose PK endpoints of treprostinil are as follows:

- AUC from time zero to 2 hours postdose (AUC0-2hr)
- AUC from time zero to 4 hours postdose (AUC0-4hr)
- AUC from time zero to 8 hours postdose (AUC0-8hr)
- AUC from time zero to 12 hours postdose (AUC0-12hr)
- AUC from time zero to 24 hours postdose (AUC0-24hr)
- AUC from time zero to the time of the last quantifiable concentration (AUC0-tlast)
- AUC0-∞
- Cmax
- tmax

- t1/2
- apparent total plasma clearance (CL/F)
- apparent volume of distribution during terminal phase  $(V_z/F)$ .

Other PK parameters may be calculated as appropriate.

### 3. INVESTIGATIONAL PLAN

#### 3.1. Overall Study Design and Plan

This will be a Phase 1, single-dose, randomized, double-blind, placebo-controlled, sequential-group study conducted at a single center. Overall, approximately 64 subjects are planned to be enrolled in 8 groups, with each group consisting of 8 subjects (Figure 2).

Potential subjects will be screened (Days -28 to -2) to confirm that they fulfil the eligibility inclusion/exclusion criteria to enter the study. After verification of eligibility, subjects will be admitted to the Clinical Research Unit (CRU) on Day -1 (Check-in; the day before dosing). Each subject will participate in 1 treatment period only and reside at the CRU from Day -1 to Day 3.

[figure not shown]
Sentinel dosing, where the first 2 subjects will be randomized 1:1 to L606 or placebo, will be used for the first 2 groups dosed. The remaining subjects in the group will be randomized 5:1 to L606 or placebo and administered study medication after the Investigator has reviewed the first 48 hours of safety data for the first 2 subjects. It is anticipated that any unanticipated safety and/or tolerability effects will be detected in the first 2 subjects dosed within a group. Sentinel dosing will not be required for subsequent groups.

All subjects will return for a Follow-up visit 7 to 10 days postdose.

Based on the ongoing review of the safety, tolerability, and PK results, additional nonresidential visits may be required. The number of additional visits per subject will not exceed 3 and will not extend beyond 28 days after dosing.

[figure not shown]
An overview of the study design is shown in Figure 1 and the planned dose levels are shown in Figure 2.

#### Figure 1: Study Schematic

The total duration of study participation for each subject (from Screening through Follow-up visit) is anticipated to be approximately 6 weeks.

#### Figure 2: Planned L606 Emitted Dose Levels

Clinical laboratory evaluations, physical examination, vital signs, safety 12-lead ECGs, the incidence and severity of AEs, and the incidence of SAEs will be monitored to assess safety and tolerability. A Schedule of Assessments is presented in Appendix 5.

Safety data (in particular those assessments which are considered for dose escalation stopping/dosing stopping criteria; Section 3.7) and PK data (as available) will be reviewed following the completion of each group. Based on this data (as well as aggregate data from previous groups), a decision will be made to proceed with:

- 1) escalation to the next higher planned dose;
- 2) repeat evaluation of the same dose in an additional group;
- 3) evaluation of a lower intermediate dose before moving on to the next higher dose; or
- 4) discontinuation of dosing.

## **3.2.** Study Start and End of Study Definitions

The start of the study is defined as the date the first enrolled subject signs an Informed Consent Form (ICF). The point of enrollment occurs at the time of subject number allocation. The end of the study is defined as the date of the last subject's last assessment (scheduled or unscheduled).

### **3.3.** Additional Groups

Following review of the safety, tolerability, and PK data, additional dose groups may be added to the study in a protocol amendment. Up to 3 further groups of 8 subjects (6 active:2 placebo) may be included. The requirement for additional groups will be agreed with the Sponsor, documented in the Trial Master File (TMF), and the Institutional Review Board will be notified of the changes.

### **3.4.** Discussion of Study Design, Including the Choice of Control Groups

A sequential-group, ascending-dose design has been chosen for safety reasons as this will be the L606 first-in-human study. Oral inhalation doses have been chosen for the study as this is the intended clinical route of administration.

Based upon the nonclinical data and clinical safety and efficacy information on the active ingredient, the duration of each treatment period is considered adequate to achieve the study objectives.

This study will be double-blind and placebo-controlled in order to avoid bias in the collection and evaluation of data during its conduct. Placebo has been chosen as the control treatment to assess whether any observed effects are treatment-related or simply reflect the study conditions.

The L606 data, along with clinical experience with treprostinil, suggest that single doses of L606 are unlikely to result in significant adverse effects in healthy subjects. Conducting the study in healthy subjects mitigates the potential confounding effects of the disease state and concomitant medications.

Sentinel dosing will be used in this study. To minimize risk, there will be an interval of at least 48 hours for evaluation of safety after the first 2 subjects have been dosed (1 with L606 and 1 with placebo) in each of the first 2 groups.

## **3.4.1. Dose Interval**

The pharmacology of treprostinil is well-characterized and approved for the treatment of PAH in 3 other formulations. L606 is being developed to accomplish high drug loading efficiency and sustained release properties, enabling a drug therapeutic effect over a prolonged time period and reducing local irritation on the respiratory tract. Because the treprostinil exposure will consequently be different from the exposure of other formulations, the safety profile cannot be entirely extrapolated to L606 (Liposomal Treprostinil Inhalation Solution). Therefore, dosing for the first 2 groups will be such that 2 subjects (1 L606 and 1 placebo) will be dosed 48 hours before the remaining 6 subjects. Dose administration of the remaining 6 subjects in the group will be at the Investigator's discretion.

## 3.5. Selection of Doses in the Study

Dose administration using an inhalation system needs to account for differences between the dose loaded into the nebulizer (loaded dose), the dose emitted from the nebulizer (emitted dose), and the dose delivered to the lung (respirable dose). For the L606 inhalation system, approximately 85% of the loaded dose is emitted and approximately 60% of the emitted dose is respirable. For comparison, approximately 80% of the dose emitted by the Tyvaso inhalation system is respirable.

The planned L606 doses were selected based on current nonclinical pharmacology and toxicology data, along with clinical data for Tyvaso (Treprostinil Inhalation Solution). The initial, recommended, and maximum tolerated emitted doses for Tyvaso, with corresponding respirable doses, are listed in Table 2. Additional clinical information for Tyvaso is summarized in Section 1.2.3.

In a Good Laboratory Practice (GLP) 28-day inhalation toxicology study, the L606 no observed adverse effect level (NOAEL) in Sprague Dawley rats was 20.0  $\mu$ g/kg (respirable dose). This corresponds to a human equivalent dose (HED) of 3.23  $\mu$ g/kg (193.55  $\mu$ g dose for a 60 kg human) as calculated from Food and Drug Administration (FDA) guidance (FDA 2005). The proposed starting emitted dose is 51  $\mu$ g L606, giving an approximately 3.8-fold safety margin compared to the HED for the NOAEL in the rat. The proposed emitted dose is expected to yield a respirable dose of 30.6  $\mu$ g, which provides an approximately 6.3-fold safety margin compared with the HED for the NOAEL in rat.

The estimated AUC ratio of NOAEL in rat to L606 starting dose in human is approximately 97-fold, which was calculated from the AUC for NOAEL in rat (55.4 ng•h/mL) divided by estimated L606 AUC at starting dose (approximately 0.57 ng•h/mL). The estimated L606 AUC at starting dose (approximately 0.57 ng•h/mL) was derived from the equality of two ratios; 1) AUC ratio of Tyvaso to L606 at starting dose in healthy volunteers (0.8 ng•h/mL) to

2) respiratory dose ratio of Tyvaso 43.2  $\mu$ g/kg (80% of emitted dose 54  $\mu$ g/kg) to L606 30.6  $\mu$ g/kg (60% of emitted dose 51  $\mu$ g/kg).

Starting dose calculations are summarized in Table 1.

	Respirable Dose	Emitted Dose	AUC (ng•hr/mL)
Rat NOAEL (28-day inhalation toxicology study)	20.0 µg/kg	-	55.4
HED	3.23 μg/kg (193.55 μg/60 kg)	-	-
Proposed Starting Dose in Humans	30.6 μg (60% of emitted dose)	51 μg	-
Estimated AUC at Starting Dose	-	-	0.57 0.8 ng•h/mL / (43.2 μg/kg / 30.6 μg/kg)
Safety Margin to Respirable HED or AUC	6.3-fold (193.55 µg / 30.6 µg)	3.8-fold (193.55 µg / 51 µg)	~97-fold (55.4 ng•h/mL / 0.57 ng•h/mL)

 Table 1:
 Summary of Starting Dose Calculations

Abbreviations: AUC = area under the plasma concentration-time curve; HED = human equivalent dose; NOAEL = no observed adverse effect level.

A non-GLP 10-day inhalation toxicity study in rats showed L606 had reduced clinical incidence during inhalation exposure compared to Tyvaso, suggesting L606 may be better tolerated. Treprostinil  $C_{max}$  is considered related to patient adverse effects both locally and systemically. Encapsulation of treprostinil in liposome improved the PK profile in terms of reducing  $C_{max}$  and exerting a stable plasma level for an extended duration (up to 8 hours). In contrast, the Tyvaso exhibited an immediate release in lung and rapid adsorption, distribution, and metabolism in plasma, resulting in high peak-trough fluctuations during a treatment session of 4 hours. L606 formulation exhibited a preferential PK profile with a comparable  $C_{max}$  value at the target dose of 48 µg/kg to that of Tyvaso at the target dose of 6 µg/kg. These results suggest the MTD for L606 could be 8 times higher than the MTD for Tyvaso. The planned maximum L606 emitted dose is 480 µg, which is expected to yield a respirable dose that is less than 4 times the Tyvaso maximum tolerated respirable dose.

Details of all doses administered will be documented in the TMF.

Treprostinil Formulation	Reference/Cohort	Loaded Dose (µg)	Loaded Volume (µL)	Emitted Dose (µg)	Respirable Dose (µg)
Tyvaso	Initial Dose			18	14.4
	Recommended Dose			54	43.2
	Maximum Tolerated Dose			84	67.2
L606 a	Cohort 1	60	40	51	30.6
	Cohort 2	120	80	102	61.2
	Cohort 3	180	120	153	91.8
	Cohort 4	240	160	204	122.4
	Cohort 5	300	200	255	153.0
	Cohort 6	360	240	306	183.6
	Cohort 7	420	280	357	214.2
	Cohort 8	480	320	408	244.8

 Table 2:
 Tyvaso Reference Doses and Planned L606 Doses

Tyvaso emitted dose  $\times 80\%$  = respirable dose (80% is the fine particle fraction of the Tyvaso inhalation system) L606 loaded dose  $\times 85\%$  = emitted dose (85% is the emission efficiency of the L606 nebulizer) L606 emitted dose  $\times 60\%$  = respirable dose (60% is the fine particle fraction of the L606 nebulizer)

a 1.5 mg active pharmaceutical ingredient (treprostinil) in 1.0 mL liposome solution

#### **3.6.** Dose Escalation

Doses will be administered in an escalating manner following satisfactory review by the Sponsor and Investigator of the safety, tolerability, and PK from the lower dose levels. Doses may be reduced and may be lower than the starting dose. There will be a minimum of 7 days between dose escalations to allow sufficient time for an adequate safety review.

Between each dose escalation, the safety data review committee, consisting of the Principal Investigator, Medical Monitor, and Sponsor's Representative, will review all available blinded data to ensure it is safe to proceed with the planned dose escalation. An interim safety report, summarizing results from all available safety assessments, will be sent to the Sponsor prior to the start of each successive dose escalation group. Any clinically significant results will be discussed with the Sponsor before dose escalation continues. Interim PK data will also be reviewed in terms of dose escalation and to confirm that the study design remains appropriate. In the event of a disagreement between Sponsor and Investigator on the dose escalation decision, the decision of the Investigator will be upheld.

## 3.7. Dose Escalation Stopping/Dosing Stopping Criteria

If any of the following scenarios occur within a group, dose escalation will be stopped, dose levels will not be repeated, and higher dose levels will not be tested:

• Clinically relevant signs or severe symptoms of similar nature occur in ≥2 subjects within a group, which in the opinion of the safety review team warrant stopping of dose escalation.

- A symptomatic drop in blood pressure from supine to standing of >20 mmHg systolic and/or >10 mmHg diastolic is seen in ≥2 subjects within a group.
- Occurrence of any SAE, which in the opinion of the Principal Investigator, is deemed to be related to study drug.
- Evidence of clinically significant increases in liver function tests (aspartate aminotransferase [AST], alanine aminotransferase [ALT], bilirubin, and gamma glutamyl transferase, defined as ALT or AST >5 × the upper limit of normal [ULN]; or ALT or AST >3 × ULN with a total bilirubin of >2 × ULN with symptoms [ie, monitor for drug-induced liver injury] compared with Day -1) in ≥2 subjects within a group (confirmed with repeat testing).
- Moderate nausea or vomiting that prevents a subject from eating a meal on 3 or more occasions on 2 successive days in ≥2 subjects within a group.
- Symptomatic decrease in supine systolic or diastolic blood pressure of ≥30 or ≥20 mmHg, respectively, from predose baseline in ≥2 subjects within a group.
- Symptomatic decrease in orthostatic systolic or diastolic blood pressure of ≥30 or ≥20 mmHg, respectively, from supine value in ≥2 subjects within a group.
- Forced expiratory volume in 1 second (FEV1) or forced vital capacity (FVC) <65% of predose baseline in ≥2 subjects within a group.
- Symptomatic bronchospasm requiring therapy in  $\geq 2$  subjects within a group.
- Incapacitating dyspnea or coughing, hypoxemia (oxygen saturation ≤90%) in ≥2 subjects within a group.
- Methemoglobin  $\geq 7\%$  in  $\geq 2$  subjects within a group.

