### 4.4. Subject Withdrawal and Replacement

A subject is free to withdraw from the study at any time. In addition, a subject will be withdrawn if any of the following criteria are met:

- change in compliance with any inclusion/exclusion criterion that is clinically relevant and affects subject safety as determined by the Investigator (or designee)
- noncompliance with the study restrictions that might affect subject safety or study assessments/objectives, as considered applicable by the Investigator (or designee)
- any clinically relevant sign or symptom that, in the opinion of the Investigator (or designee), warrants subject withdrawal.

If a subject is withdrawn, the Sponsor will be notified and the date and reason(s) for the withdrawal will be documented in the subject's electronic Case Report Form. If a subject is withdrawn, efforts will be made to perform all follow-up assessments, if possible (Appendix 5). Other procedures may be performed at the Investigator's (or designee's) and/or Sponsor's discretion. If the subject is in-house, these procedures should be performed before the subject is discharged from the clinic. The Investigator (or designee) may also request that the subject return for an additional Follow-up visit. All withdrawn subjects will be followed until resolution of all their AEs or until the unresolved AEs are judged by the Investigator (or designee) to have stabilized.

Subjects who are withdrawn for reasons not related to study drug may be replaced following discussion between the Investigator and the Sponsor. Subjects withdrawn as a result of AEs thought to be related to the study drug will generally not be replaced.

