### 5.2. Study Treatment Administration

Each dose of L606 and placebo solution will be self-administered by the subject via oral inhalation. The entire treatment procedure will be completed within 10 minutes.

Subjects will be administered the IMP in numerical order while seated and may be semi-recumbent but will not be permitted to lie supine for 2 hours after dosing, except as necessitated by the occurrence of an AE(s) and/or study procedures.

The planned emitted dose escalation groups are:

- Cohort 1: 51 µg L606 or placebo volume equivalent to 51 µg
- Cohort 2: 102 μg L606 or placebo volume equivalent to 102 μg
- Cohort 3: 153 µg L606 or placebo volume equivalent to 153 µg
- Cohort 4: 204 µg L606 or placebo volume equivalent to 204 µg
- Cohort 5: 255 µg L606 or placebo volume equivalent to 255 µg
- Cohort 6: 306 µg L606 or placebo volume equivalent to 306 µg
- Cohort 7: 357  $\mu$ g L606 or placebo volume equivalent to 357  $\mu$ g
- Cohort 8: 408 µg L606 or placebo volume equivalent to 408 µg

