### 8.5. Interim Analysis

Between each dose escalation the safety data review committee, consisting of the Principal Investigator, Medical Monitor, and Sponsor's Representative, will review all available blinded data to ensure it is safe to proceed with the planned dose escalation. An interim safety report, summarizing results from all available safety assessments, will be sent to the Sponsor prior to the start of each successive treatment period. Any clinically significant results will be discussed with the Sponsor before dose escalation continues. Interim PK data will also be reviewed in terms of dose escalation and to confirm that the study design remains appropriate.

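### Section 3.7 is headed as a dosing stopping rule, but a met criterion does not require a hold on undosed subjects in the same group

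*Protocol*

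**What the plan says.** Section 3.7 (Dose Escalation Stopping/Dosing Stopping Criteria) lists 11 criteria. If any is met within a group, "dose escalation will be stopped, dose levels will not be repeated, and higher dose levels will not be tested".

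Other sections bear on what happens inside a group:

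- **Section 3.1, review options (below Figure 2).** The option to repeat a dose is worded "repeat evaluation of the same dose in an additional group". Safety data "will be reviewed following the completion of each group", and discontinuation of dosing is one outcome of that review.
- **Sections 3.6 and 8.5.** Between escalations the committee "will review all available blinded data to ensure it is safe to proceed with the planned dose escalation". Section 8.5 has the same timing: "Between each dose escalation the safety data review committee".
- **Sections 3.1 and 3.4.1.** In groups 1 and 2 a sentinel pair (1 L606, 1 placebo) is dosed 48 hours before the other six, whose dosing is then at the Investigator's discretion. For later groups, "Sentinel dosing will not be required for subsequent groups".
- **Section 5.2.** "Subjects will be administered the IMP in numerical order while seated". No interval between subjects is stated.
- **Section 4.4.** Grounds for withdrawal include "any clinically relevant sign or symptom that, in the opinion of the Investigator (or designee), warrants subject withdrawal". This acts on the affected subject.
- **Section 4.5.** The Investigator, Sponsor or Medical Monitor may discontinue the study on listed grounds. The list does not refer to Section 3.7.

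**The concern.** A stopping rule in a first-in-human study is meant to replace judgment under pressure with a pre-agreed action. The heading of Section 3.7 promises this for dosing, but the sentence beneath it delivers it only for later groups.

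Followed as written, a drug-related SAE in one subject closes that dose to every new group while leaving it open to the next subject in the same group. Two symptomatic falls in blood pressure would have the same effect. Whether the next subject inhales the dose then depends on someone choosing to intervene.

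**Working it through.** The protocol gives no operating figure for the stopping rule, so there is nothing to reproduce. The check is mainly textual, followed by a bound and an illustration.

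**1. Does any provision require a within-group hold?**

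| Provision | Acts on | Mandatory within the group? |
|---|---|---|
| 3.7 consequence sentence | Escalation, repeat level, higher levels | No |
| 3.1 review, 3.6, 8.5 | After group completion or between escalations | No |
| 3.1 and 3.4.1 sentinel | Groups 1 and 2 only; release of the other six is discretionary | No |
| 4.4 | The affected subject | No |
| 4.5 | Whole study, discretionary | No |

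**2. Which criteria can be met while subjects are still undosed?** This assumes a group (after any sentinel pair) is dosed on one day.

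- On Day 1: 6 of the 11 bullets. These are the related SAE, the supine-to-standing drop, the supine decrease, the orthostatic decrease, bronchospasm, and incapacitating dyspnea or coughing. The orthostatic decrease (≥30/≥20 mmHg) lies inside the supine-to-standing drop (>20/>10 mmHg), so there are 5 distinct triggers. If the loosely punctuated dyspnea bullet also requires hypoxemia, Day 1 detection needs unscheduled oximetry.
- Dependent on the safety review team's opinion: 1 (the first bullet).
- Usually from Day 2 only: 4. By the Schedule of Assessments, post-dose laboratory tests, spirometry and methemoglobin start on Day 2, and the nausea/vomiting criterion needs 2 successive days.
- 6 + 1 + 4 = 11.

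**3. Bound.** Groups have 8 subjects.

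- The related SAE needs one subject: 8 − 1 = 7 undosed at most.
- Every other acute criterion needs at least two: 8 − 2 = 6 at most.
- In groups 1 and 2, at most 8 − 2 = 6 subjects follow the sentinel pair. The pair has one L606 recipient, so drug effect in the pair alone cannot meet a two-subject criterion.

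**4. Dependence on the dosing interval.** Assume subject k starts at (k − 1)d minutes and the first two subjects both meet a blood pressure criterion at their first scheduled check. Checks count from the end of inhalation. With a full 10-minute inhalation, the first supine check is 10 + 15 = 25 minutes after the start and the first orthostatic check is 10 + 60 = 70 minutes after it. The criterion is met at t = d + 25 or t = d + 70, and undosed = 8 − min(8, floor(t/d) + 1).

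| Assumed d | Supine | Orthostatic |
|---|---|---|
| All together | 0 | 0 |
| 10 min | 4 | 0 |
| 30 min | 6 | 4 |
| 60 min | 6 | 5 |

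These are not upper bounds. Inhalation may take less than 10 minutes: at 2 minutes with d = 10, t = 10 + 2 + 15 = 27 and 5 subjects are undosed. Unscheduled checks could also come earlier, and later events leave fewer undosed.

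**5. A less extreme illustration.** Assume L606 subjects are dosed one at a time, each event is seen before the next dose, the event rate on L606 is p, and the placebo rate is 0. The chance that a two-subject criterion is met among 6 L606 subjects is 1 − (1 − p)^6 − 6p(1 − p)^5. It is met at the j-th L606 subject with probability (j − 1)p²(1 − p)^(j−2), leaving 6 − j. The mean left, given that it is met, is the sum of these products over j = 2 to 6, divided by the first formula.

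| p | P(met) | Mean L606 subjects undosed, if met |
|---|---|---|
| 5% | 3.3% | 1.4 |
| 10% | 11.4% | 1.5 |
| 20% | 34.5% | 1.7 |
| 30% | 58.0% | 1.9 |
| 50% | 89.1% | 2.5 |

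For p = 50%: 4(0.25) + 3(0.25) + 2(0.1875) + 1(0.125) = 2.25, and 2.25 / 0.891 = 2.5.

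**The case against.** The strongest reply is that the bar on repeating a dose level may be intended to cover undosed subjects of the current group, which would satisfy the heading. That intention is possible, but Section 3.1 defines a repeat as a further group, so the sentence is at best unclear and the same clause repairs it.

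A reader might infer that nobody can stop dosing mid-group. The documents do not support that. Section 4.5 lets the Investigator, Sponsor or Medical Monitor discontinue for new or more severe adverse events and does not tie this to group completion. Section 5.4 lets the Investigator unblind to manage subject safety, dosing is supervised in the unit, and Appendix 4 exempts changes that remove an immediate hazard from prior IRB approval. This part of the objection stands: the gap is between may and must.

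A reader might also take the 48 subjects planned for groups 3 to 8 (6 × 8, of 64) as the number exposed. That is not supported. Once a criterion is met, repeats and higher levels are barred, so the gap bites in the one group being dosed.

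Nor is the gap confined to groups 3 to 8. The six subjects dosed after a sentinel pair face it too.

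**Conclusion.** The concern holds as a missing mandatory hold in Section 3.7, and it should be fixed. It applies to any group and is widest in groups 3 to 8.

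The firm figure is the bound: at most 7 subjects of one group after a related SAE in the first subject dosed, or at most 6 after a two-subject criterion. The practical number lies between 0 (whole group dosed together) and that bound. It cannot be narrowed from the protocol, because the interval between subjects is not stated. The interval and event-rate tables rest on assumed inputs and show only that the number need not be zero.

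The conclusion that only some criteria matter assumes same-day dosing of the group. If dosing were spread over days, the Day 2 criteria would matter too.

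**What to change.** Add to the consequence sentence in Section 3.7: *and dosing of all remaining subjects in the current group will be suspended immediately; it will not resume unless the safety data review committee determines that the criterion was not in fact met as defined here.*

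Leave unblinding to the Investigator under Section 5.4. Resumption should not depend on whether the affected subjects received L606. Section 3.7 counts subjects regardless of arm, so a group could otherwise continue at a dose already closed to escalation and repetition, and committee review under Section 3.6 is blinded.

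The cost is one clause by amendment, with IRB approval, and no added subjects or scheduled assessments. In use, it may mean a pause, an unscheduled committee review if resumption is sought, or an incomplete group.
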